1.1 Does the protocol specify timelines for				
1.1.1 Start of data collection ¹				6
1.1.2 End of data collection ²				6
1.1.3 Study progress report(s)				
1.1.4 Interim progress report(s)				
1.1.5 Registration in the EU PAS register				6
1.1.6 Final report of study results.				6

Comments:

Section 2: Research question	Yes	No	N/A	Section Number
2.1 Does the formulation of the research question and objectives clearly explain:				8
2.1.1 Why the study is conducted? (e.g. to address an important public health concern, a risk identified in the risk management plan, an emerging safety issue)				7
2.1.2 The objective(s) of the study?				8
2.1.3 The target population? (i.e. population or subgroup to whom the study results are intended to be generalised)				8
2.1.4 Which hypothesis(-es) is (are) to be tested?				
2.1.5 If applicable, that there is no a priori hypothesis?				9.5

Comments:

The study is not designed to confirm (or refute) any pre-defined hypotheses.

¹ Date from which information on the first study is first recorded in the study dataset or, in the case of secondary use of data, the date from which data extraction starts.

² Date from which the analytical dataset is completely available.

Section 3: Study design	Yes	No	N/A	Section Number
3.1 Is the study design described? (e.g. cohort, case-control, cross-sectional, new or alternative design)				9.1
3.2 Does the protocol specify whether the study is based on primary, secondary or combined data collection?				9.1; 9.4
3.3 Does the protocol specify measures of occurrence? (e.g. incidence rate, absolute risk)				9.3.3
3.4 Does the protocol specify measure(s) of association? (e.g. relative risk, odds ratio, excess risk, incidence rate ratio, hazard ratio, number needed to harm (NNH) per year)				
3.5 Does the protocol describe the approach for the collection and reporting of adverse events/adverse reactions? (e.g. adverse events that will not be collected in case of primary data collection)				11

Comments:

Statistical analyses will be of exploratory and descriptive in nature.

Section 4: Source and study populations	Yes	No	N/A	Section Number
4.1 Is the source population described?				9.2.2
4.2 Is the planned study population defined in terms of:				
4.2.1 Study time period?				9.2.3
4.2.2 Age and sex?				9.2.2
4.2.3 Country of origin?				9.2.2
4.2.4 Disease/indication?				9.2.2
4.2.5 Duration of follow-up?				9.2.2
4.3 Does the protocol define how the study population will be sampled from the source population? (e.g. event or inclusion/exclusion criteria)				9.2.2-4

Comments:

Section 5: Exposure definition and measurement	Yes	No	N/A	Section Number
5.1 Does the protocol describe how the study exposure is defined and measured? (e.g. operational details for defining and categorising exposure, measurement of dose and duration of drug exposure)				9.3.2
5.2 Does the protocol address the validity of the exposure measurement? (e.g. precision, accuracy, use of validation sub-study)				9.3.2; 9.9

Section 5: Exposure definition and measurement	Yes	No	N/A	Section Number
5.3 Is exposure classified according to time windows? (e.g. current user, former user, non-use)				9.3.2
5.4 Is exposure classified based on biological mechanism of action and taking into account the pharmacokinetics and pharmacodynamics of the drug?				9.3.2

Comments:

--

Section 6: Outcome definition and measurement	Yes	No	N/A	Section Number
6.1 Does the protocol specify the primary and secondary (if applicable) outcome(s) to be investigated?				9.3.3
6.2 Does the protocol describe how the outcomes are defined and measured?				9.3.3
6.3 Does the protocol address the validity of outcome measurement? (e.g. precision, accuracy, sensitivity, specificity, positive predictive value, prospective or retrospective ascertainment, use of validation sub-study)				9.9
6.4 Does the protocol describe specific endpoints relevant for Health Technology Assessment? (e.g. HRQoL, QALYs, DALYs, health care services utilisation, burden of disease, disease management)				

Comments:

There are no Health Technology Assessments planned for this study.

Section 7: Bias	Yes	No	N/A	Section Number
7.1 Does the protocol describe how confounding will be addressed in the study?				9.9
7.1.1. Does the protocol address confounding by indication if applicable?				
7.2 Does the protocol address:				
7.2.1. Selection biases (e.g. healthy user bias)				
7.2.2. Information biases (e.g. misclassification of exposure and endpoints, time-related bias)				
7.3 Does the protocol address the validity of the study covariates?				9.7.2; 9.8

Comments:

--

Section 8: Effect modification	Yes	No	N/A	Section Number

Section 8: Effect modification	Yes	No	N/A	Section Number
8.1 Does the protocol address effect modifiers? (e.g. collection of data on known effect modifiers, sub-group analyses, anticipated direction of effect)				

Comments:

Section 9: Data sources	Yes	No	N/A	Section Number
9.1 Does the protocol describe the data source(s) used in the study for the ascertainment of:				
9.1.1 Exposure? (e.g. pharmacy dispensing, general practice prescribing, claims data, self-report, face-to-face interview)				9.3.2
9.1.2 Outcomes? (e.g. clinical records, laboratory markers or values, claims data, self-report, patient interview including scales and questionnaires, vital statistics)				9.3.3
9.1.3 Covariates?				9.3.1
9.2 Does the protocol describe the information available from the data source(s) on:				
9.2.1 Exposure? (e.g. date of dispensing, drug quantity, dose, number of days of supply prescription, daily dosage, prescriber)				9.3.2
9.2.2 Outcomes? (e.g. date of occurrence, multiple event, severity measures related to event)				9.3.3
9.2.3 Covariates? (e.g. age, sex, clinical and drug use history, co-morbidity, co-medications, lifestyle)				9.3.1
9.3 Is a coding system described for:				
9.3.1 Exposure? (e.g. WHO Drug Dictionary, Anatomical Therapeutic Chemical (ATC) Classification System)				9.3.2
9.3.2 Outcomes? (e.g. International Classification of Diseases (ICD)-10, Medical Dictionary for Regulatory Activities (MedDRA))				9.3.3
9.3.3 Covariates?				9.3.1
9.4 Is a linkage method between data sources described? (e.g. based on a unique identifier or other)				

Comments:

Section 10: Analysis plan	Yes	No	N/A	Section Number
10.1 Is the choice of statistical techniques described?				9.7
10.2 Are descriptive analyses included?				9.7
10.3 Are stratified analyses included?				9.7

Section 10: Analysis plan	Yes	No	N/ A	Section Number
10.4 Does the plan describe methods for adjusting for confounding?				
10.5 Does the plan describe methods for handling missing data?				9.7.3
10.6 Is sample size and/or statistical power estimated?				9.5

Comments:

Section 11: Data management and quality control	Yes	No	N/ A	Section Number
11.1 Does the protocol provide information on data storage? (e.g. software and IT environment, database maintenance and anti-fraud protection, archiving)				9.8
11.2 Are methods of quality assurance described?				9.8
11.3 Is there a system in place for independent review of study results?				9.8

Comments:

Section 12: Limitations	Yes	No	N/ A	Section Number
12.1 Does the protocol discuss the impact on the study results of: 12.1.1 Selection bias? 12.1.2 Information bias? 12.1.3 Residual/unmeasured confounding? (e.g. anticipated direction and magnitude of such biases, validation sub-study, use of validation and external data, analytical methods)	  	  	  	9.9 9.9 9.9
12.2 Does the protocol discuss study feasibility? (e.g. study size, anticipated exposure, duration of follow-up in a cohort study, patient recruitment)				9.2

Comments:

Section 13: Ethical issues	Yes	No	N/ A	Section Number
13.1 Have requirements of Ethics Committee/ Institutional Review Board been described?				9.10.1
13.2 Has any outcome of an ethical review procedure been addressed?				
13.3 Have data protection requirements been described?				10

Proprietary confidential information © 2021 Boehringer Ingelheim International GmbH or one or more of its affiliated companies

Comments:

Section 14: Amendments and deviations	Yes	No	N/ A	Section Number
14.1 Does the protocol include a section to document amendments and deviations?				5

Comments:

[figure not shown]
Section 15: Plans for communication of study results	Yes	No	N/ A	Section Number
15.1 Are plans described for communicating study results (e.g. to regulatory authorities)?				12
15.2 Are plans described for disseminating study results externally, including publication?				12

Comments:

ANNEX 3. ADDITIONAL INFORMATION

COPD Assessment Test (CAT) (9)

Your name:	Today's date:
------------	---------------

How is your COPD? Take the COPD Assessment Test™ (CAT)

This questionnaire will help you and your healthcare professional measure the impact COPD (Chronic Obstructive Pulmonary Disease) is having on your wellbeing and daily life. Your answers, and test score, can be used by you and your healthcare professional to help improve the management of your COPD and get the greatest benefit from treatment.

For each item below, place a mark (X) in the box that best describes you currently. Be sure to only select one response for each question.

Example: I am very happy 0 1 2 3 4 5 I am very sad

						SCORE				
I never cough			0	1	2	3	4	5	I cough all the time	
I have no phlegm (mucus) in my chest at all			0	1	2	3	4	5	My chest is completely full of phlegm (mucus)	
My chest does not feel tight at all			0	1	2	3	4	5	My chest feels very tight	
When I walk up a hill or one flight of stairs I am not breathless			0	1	2	3	4	5	When I walk up a hill or one flight of stairs I am very breathless	
I am not limited doing any activities at home			0	1	2	3	4	5	I am very limited doing activities at home	
I am confident leaving my home despite my lung condition			0	1	2	3	4	5	I am not at all confident leaving my home because of my lung condition	
I sleep soundly			0	1	2	3	4	5	I don't sleep soundly because of my lung condition	
I have lots of energy			0	1	2	3	4	5	I have no energy at all	
TOTAL SCORE 										

EQ-5D-5L questionnaire (23,24)

Under each heading, please tick the ONE box that best describes your health TODAY.

MOBILITY

- I have no problems in walking about
I have slight problems in walking about
I have moderate problems in walking about
I have severe problems in walking about
I am unable to walk about

SELF-CARE

- I have no problems washing or dressing myself
I have slight problems washing or dressing myself
I have moderate problems washing or dressing myself
I have severe problems washing or dressing myself
I am unable to wash or dress myself

USUAL ACTIVITIES (e.g. work, study, housework, family or leisure activities)

- I have no problems doing my usual activities
I have slight problems doing my usual activities
I have moderate problems doing my usual activities
I have severe problems doing my usual activities
I am unable to do my usual activities

PAIN / DISCOMFORT

[figure not shown]
- I have no pain or discomfort
I have slight pain or discomfort
I have moderate pain or discomfort
I have severe pain or discomfort
I have extreme pain or discomfort

ANXIETY / DEPRESSION

- I am not anxious or depressed
I am slightly anxious or depressed
I am moderately anxious or depressed
I am severely anxious or depressed
I am extremely anxious or depressed

- We would like to know how good or bad your health is TODAY.
- This scale is numbered from 0 to 100.
- 100 means the best health you can imagine.
0 means the worst health you can imagine.
- Mark an X on the scale to indicate how your health is TODAY.
- Now, please write the number you marked on the scale in the box below.

YOUR HEALTH TODAY =

Simplified Medication Adherence Questionnaire (SMAQ) (25)

-
1. Do you ever forget to take the medication? Yes...No
-
2. Do you always take the medication at the specified time? Yes....No
-
3. Do you ever stop taking the medication if you feel ill? Yes....No
-
4. Did you forget to take the medication during the weekend? Yes....No
-
5. In the last week, How many times did you not take a dose?
- A: None of the above
B: 1-2
C: 3-5
D: 6-10
E: Greater than 10
-
6. Since the last medical visit, how many full days did you not take the medication? Number of days:
-

Modified Medical Research Council (mMRC) questionnaire ([26](#))

Please circle the number which best describes your grade of breathlessness:

I only get breathless with strenuous exercise. 0

I get short of breath when hurrying on level ground or walking up a slight hill. 1

On level ground, I walk slower than people of the same age because of breathlessness, or have to stop for breath when walking at my own pace. 2

I stop for breath after walking about 100 yards or after a few minutes on level ground. 3

I am too breathless to leave the house or I am breathless when dressing. 4

Patient satisfaction and preference questionnaire (PASAPQ) (29)

**PATIENT SATISFACTION
AND PREFERENCE QUESTIONNAIRE**

PASAPQ

Direct version

PART 1: RATING OF SATISFACTION WITH INHALER ATTRIBUTES

Instructions: For the following questions, please check the response that best describes how satisfied you are with each of the following items. Please take as much time as you need to answer each question.

How satisfied are you...	Inhaler	Very Dissatisfied		Dissatisfied		Somewhat Dissatisfied		Neither Satisfied nor Dissatisfied		Somewhat Satisfied		Satisfied		Very Satisfied		
																
1. With the overall feeling of inhaling your medicine?	Inhaler															
2. With the feeling that the inhaled dose goes to your lungs?	Inhaler															
3. That you can tell the amount of medication left in your inhaler?	Inhaler															
4. That the inhaler works reliably?	Inhaler															
5. With the ease of inhaling a dose from the inhaler?	Inhaler															
6. With the instructions for use?	Inhaler															
7. With the size of your inhaler?	Inhaler															
8. That the inhaler is durable (hard wearing)?	Inhaler															

Please go to the next page

		Very Dissatisfied	Dissatisfied	Somewhat Dissatisfied	Neither Satisfied nor Dissatisfied	Somewhat Satisfied	Satisfied	Very Satisfied
9.	With the ease of cleaning your inhaler?	Inhaler						
10.	With using the inhaler?	Inhaler						
11.	With the speed at which medicine comes out of the inhaler?	Inhaler						
12.	With the ease of holding the inhaler during use?	Inhaler						
13.	With the overall convenience of carrying the inhaler with you?	Inhaler						
14.	Overall, how satisfied are you with your inhaler?	Inhaler						

▼ *Please go to the next page*

**PART II: RATING OF PREFERENCE AND WILLINGNESS TO CONTINUE
WITH INHALER**

Comparing the two inhalers that you have used, overall, would you prefer to use Inhaler 1 or Inhaler 2?

Please check one box

I prefer Inhaler 1

I prefer Inhaler 2

No preference

How would you feel about continuing to use the inhaler?

Please indicate your willingness to continue using the inhaler that you used during the study by providing a value between 1 and 100.

0 indicates that you would not be willing to continue using the inhaler and 100 indicates that you would definitely be willing to continue.

Please write in a number in the box that is between 0 and 100.

Inhaler

**THANK YOU VERY MUCH
FOR COMPLETING THIS
SURVEY.**

**PLEASE RETURN THIS SURVEY
TO THE
STUDY COORDINATOR.**

## **2. LIST OF ABBREVIATIONS**

ADR	Adverse Drug Reaction
AE	Adverse Event
AESI	Adverse Event of Special interest
BI	Boehringer Ingelheim
CA	Competent Authority
CAT	COPD Assessment Test
CCDS	Company Core Data Sheet
CI	Confidence Interval
CTM	Clinical Trial Manager
COPD	Chronic Obstructive Pulmonary Disease CRA
CRF	Case Report Form
CTCAE	Common Terminology Criteria for Adverse Events CTP
DMRP	Data management and review plan
DMP	Data Management Plan
eCRF	Electronic Case Report Form
EMA	European Medicines Agency
ENCePP	European Network of Centers for Pharmacoepidemiology and Pharmacovigilance
EQ-5D-5L	EuroQoL-5D-5L questionnaire EU
FDA	Food and Drug Administration
FDC	Fix Dose Combination
FEV1	Forced expiratory volume in one second GCP
GEP	Good Epidemiological Practice
GPP	Good Pharmacoepidemiology Practice
GVP	Good Pharmacovigilance Practices
GOLD	Global Initiative for Chronic Obstructive Lung Disease HCPs
IB	Investigator's Brochure
ICH	International Conference on Harmonization
ICS	Inhaled Corticosteroids
IEC	Independent Ethics Committee
ISF	Investigator Site File
IQR	Interquartile range
LABA	Long-acting beta 2 adrenoceptor agonist LAMA
MedDRA	Medical Dictionary for Drug Regulatory Activities mMRC
NIS	Non-Interventional Study
PASAPQ	Abbreviated Patient Satisfaction Questionnaire PASS
PGE	Physician's Global Evaluation
SAE	Serious Adverse Event
SAP	Statistical Analysis Plan
SEAP	Statistical and epidemiological analysis plan
SD	Standard Deviation
SDV	Source data verification
SMAQ	Simplified Medication Adherence Questionnaire SmPC
WHO	World Health Organization

### **4. PURPOSE AND SCOPE**

As per ICH E9, the purpose of this document is to provide a more technical and detailed elaboration of the principal features of the analysis described in the protocol, and to include detailed procedures for executing the statistical analysis of the primary and secondary variables and other data.

This SEAP assumes familiarity of the SEAP reviewers with the NIS protocol. In particular, the SEAP is based on the planned analysis specification as written in NIS protocol Section 9.7 "Data Analysis". Therefore, SEAP readers may consult the NIS protocol for more background information on the study, e.g., on study objectives, study design and population, treatments, definition of measurements and variables, planning of sample size.

### **5. AMENDMENTS AND UPDATES**

#### **5.1 Changes from protocol analysis**

Additional modifications from the CTP made in this SEAP:

- It was stated in CTP to exclude patients with missing values. Missing values will be treated in a different way according to their nature. Missing values due to Intercurrent Event (IE) are taken care at the estimands definitions, on the other hand, missing values not related to IE will be multiple imputed if missingness is greater than 25% for a specific variable.
- It was suggested in the CTP, [REDACTED]  
[REDACTED]
- To assess the potential associations between patient characteristics, treatment, preference [REDACTED]ing

to health status assessed with CAT will not be assessed via univariate methods, however the applicable [REDACTED] are included to the statistical models in the primary and the first secondary endpoint analysis.

[REDACTED]

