9.5 STUDY SAMPLE SIZE

The sample size determination is not based on a power calculation because no hypotheses will be tested. The primary endpoint of change in score of COPD Assessment Test (CAT) within three months after the switch from Spiriva® Handihaler® to Spiolto® Respimat® will be analysed descriptively by mean and 95% confidence interval. From other studies a mean difference in CAT score of 1.0 and standard deviation of 9.0 are expected.

With a sample size of 1310, a two-sided 95% confidence interval for the difference in paired mean scores will have an interval that extends by no more than 0.5 from the observed difference in means (e.g. an interval from 0.5 to 1.5 for a difference of 1.0), with 90% coverage probability, assuming that the true standard deviation of differences is 9.0 and that the confidence interval is based on the t statistic. The calculation was performed using the MOC3 routine from commercial software nQuery Advisor® 7.0 (██████████ [R15-1331]). To account for a 15% dropout rate, 1507 patients will be needed. Therefore, it was decided to enroll 1500 patients in the study.

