### **10.2 Handling of Missing Values**

If missingness is more than 25% for a specific outcome [REDACTED] methodologies will be examined. More specific information is provided in Section

11.3.1

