#### 11.2.1 Analysis of primary outcome.

11.2.1.1 Mean change in patients' quality of life (QoL) according to the total score of COPD Assessment Test (CAT) within three months after the switch from Spiriva® Handihaler® to Spiolto® Respimat®.

The primary estimand is defined as follows:

- A. Population: Is defined through inclusion/exclusion criteria of the study protocol to reflect the target population.
- B. Variable: Continuous variable response.

- C. Intercurrent Event (IE): Include death, drop-out due to any adverse event (AE) and treatment discontinuation. For patients experiencing an IE, the most extreme unfavourable value will be assigned (CAT score at 3 Months equals to 40).
- D. Population level summary: The change from Baseline of total CAT score within 3 Months.

Mixed model for repeated measurements (MMRM) assuming random missingness will be fitted. The dependent variable will be the CAT score at each visit. Visit, GOLD group, smoking habits, packyears, sex, age, and comorbidities appearing at a rate greater than 5% will be entered as covariates. Patients will be fitted at random and an unstructured covariance matrix will be used, allowing adjustment for correlations between study visits within the study patients. The Kenward- Roger degrees of freedom approximation will be used in the model (ddfm=kr).

Summaries of the estimated mean change from baseline of CAT score at 3 Months will be provided with 95% confidence interval. Model information will be provided as footnote under the corresponding table.

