### **11.2.2 Analysis of Secondary outcomes.**

#### **11.2.2.1 Change in the proportion of patients with COPD Assessment Test (CAT) $\geq 10$ (representing impaired health status) within three months after the switch**

Estimand:

- A. Population: Is defined through inclusion/exclusion criteria of the study protocol to reflect the target population.
- B. Variable: Binary variable response. Response is defined as having CAT score  $\geq 10$ .
- C. Intercurrent Event (IE): Include death, drop-out due to any adverse event (AE) and treatment discontinuation. For patients experiencing an IE, the most extreme unfavourable value will be assigned (patient CAT score  $\geq 10$ ).
- D. Population Level Summary: Odds ratio of response within 3 Months.

This endpoint will be analysed with a logistic GEE model with CAT response as dependent variable. Visit, GOLD group, smoking habits, packyears, sex, age, and comorbidities appearing at a rate greater than 5% will be entered as covariates and unstructured covariance matrix will be used.

Summaries of the estimated OR will be provided with 95% confidence interval. Model information will be provided as footnote under the corresponding table.

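### Multiple imputation starts only above 25% missing although 15% dropout is planned, so at the planned rate the GEE outcomes are unimputed and open to a small-to-moderate bias

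*SAP*

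**What the plan says.** SAP 5.1 replaces the protocol's exclusion of patients with missing values by a two-part rule. Values missing through an intercurrent event (death, dropout due to an adverse event, treatment discontinuation) are dealt with in the estimands, which assign the worst value. For the rest, "missing values not related to IE will be multiple imputed if missingness is greater than 25% for a specific variable".

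SAP 10.2 repeats the threshold but words it by outcome, "If missingness is more than 25% for a specific outcome", and says only that methods will be examined. It then points elsewhere: "More specific information is provided in Section" 11.3.1, which cannot be read in the public text.

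Protocol 9.5 sets the expected loss: "To account for a 15% dropout rate, 1507 patients will be needed". It continues: "Therefore, it was decided to enroll 1500 patients in the study".

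The primary MMRM (SAP 11.2.1.1) is declared to assume random missingness. For CAT ≥10 (SAP 11.2.2.1), "This endpoint will be analysed with a logistic GEE model with CAT response as dependent variable". The five EQ-5D-5L dimensions (SAP 11.2.2.3) use an ordinal logistic GEE. Neither GEE section states a missingness assumption, weights or imputation. All these models use visit, GOLD group, smoking, pack-years, sex and age, and "comorbidities appearing at a rate greater than 5% will be entered as covariates". No readable section says what happens to a patient with a missing covariate.

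**The concern.** Whether missing data cause bias depends on why they are missing, not on whether they exceed a fixed share, and the SAP gives no reason for 25%. Because the threshold lies above the planned dropout, the safeguard would not operate in the study as designed.

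Two linked outcomes are then treated differently. The CAT score is analysed by a likelihood model that tolerates loss depending on the observed baseline score. CAT ≥10, a dichotomy of that same score, is analysed by unweighted GEE, which has no such general protection. If sicker patients are lost more often, the fall in the proportion with impaired health is overstated; if fitter patients are lost, it is understated. SAP 6 says the results are to support an improvement after the switch, so the first direction matters more.

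The lack of a covariate rule leaves open who enters the models. SAP 8 collects smoking status with Never and Unknown levels, while SAP 8.3 lists only current and past smokers as covariate levels. The SAP's baseline characteristics table summarises pack-years for past and current smokers only, so the value for a never smoker is undefined.

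**Working it through.** **1. The plan's own figures.** Protocol 9.5 states: "With a sample size of 1310, a two-sided 95% confidence interval for the difference in paired mean scores" extends by no more than 0.5, with 90% coverage probability and SD of differences 9.0. The smallest n with P(t(0.975, n−1)·S/√n ≤ 0.5) ≥ 0.90 is 1310 (probability 0.901), so it reproduces. Dropout: 1310 × 1.15 = 1506.5, rounded up to 1507.

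**2. Trigger against plan.** 0.25 × 1500 = 375, so imputation needs more than 375 patients missing on a variable. Planned dropout is 0.15 × 1500 = 225, and the non-IE part is smaller still. The trigger is not reached.

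**3. What the two-visit GEE estimates.** Let p1 be the baseline proportion with CAT ≥10 in all patients, and c1 and c2 the baseline and Month-3 proportions among those with a Month-3 value. With visit as the only term and an unstructured working correlation r, the GEE solution is

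p2 = c2 + b·(p1 − c1), where b = r·√[p2(1−p2) / p1(1−p1)].

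This corrects for imbalance in baseline *status* (≥10 or not), but not for imbalance in the score within each status group.

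**4. Inputs.** Month-3 dropout of 15% is from Protocol 9.5, here all taken as non-IE. The fall of 1.0 is the protocol's expected mean difference, taken as improvement. Assumptions, because the documents do not give them: CAT roughly normal with means 14 and 13, SD 7 at both visits, and dropout logistic in baseline CAT with slope ±0.7 or ±1.2 per SD. For the correlation ρ:
- With SD 7 at both visits, SD of change 9.0 requires 81 = 2 × 49 × (1 − ρ), so ρ = 0.17.
- The alternative ρ = 0.6 implies SD of change 7 × √0.8 = 6.26, below the protocol's 9.0.

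**5. Truth.** Φ(3/7) − Φ(4/7) = 0.666 − 0.716 = −5.0 points, OR 0.79.

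**6. Results at 15% loss** (integration over the baseline distribution).

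| ρ | Who leaves, slope | c1 | c2 | b | GEE change | Bias (points) | OR |
|---|---|---|---|---|---|---|---|
| 0.17 | sicker, 0.7 | 0.687 | 0.660 | 0.109 | −5.3 | −0.3 | 0.78 |
| 0.17 | sicker, 1.2 | 0.676 | 0.657 | 0.107 | −5.5 | −0.5 | 0.77 |
| 0.17 | fitter, 0.7 | 0.754 | 0.672 | 0.096 | −4.8 | +0.3 | 0.80 |
| 0.17 | fitter, 1.2 | 0.777 | 0.676 | 0.087 | −4.6 | +0.4 | 0.80 |
| 0.6 | sicker, 0.7 | 0.687 | 0.646 | 0.428 | −5.8 | −0.8 | 0.76 |
| 0.6 | sicker, 1.2 | 0.676 | 0.636 | 0.428 | −6.3 | −1.3 | 0.75 |
| 0.6 | fitter, 0.7 | 0.754 | 0.689 | 0.373 | −4.2 | +0.9 | 0.82 |
| 0.6 | fitter, 1.2 | 0.777 | 0.702 | 0.341 | −3.5 | +1.5 | 0.85 |

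Example, row 6: 0.6358 + 0.4278 × (0.7161 − 0.6762) = 0.653; 0.653 − 0.716 = −6.3 points.

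**7. Other loss rates.** At an assumed 8% non-IE loss the bias is 0.1 to 0.3 points (ρ = 0.17) or 0.4 to 0.8 (ρ = 0.6). At 25%, the most the SAP leaves unimputed, it is 0.4 to 0.8 or 1.2 to 2.7.

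**8. Dropout depending only on baseline CAT ≥10 status.** With log odds ratio ±1 and 15% loss, the bias is at most 0.1 point at either correlation.

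**9. Scale.** With 1500 × 0.85 = 1275 pairs, the half-width for the change is about 1.96 × √[(0.203 + 0.222 − 2r × 0.213)/1275]: 3.4 points for r = 0.10 (ρ = 0.17) and 2.8 for r = 0.40 (ρ = 0.6).

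No size was computed for the EQ-5D-5L dimensions; the argument is the same.

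**The case against.** The strongest reply is that little is at stake. Deaths, adverse-event dropouts and treatment discontinuations get the worst value, and Protocol 9.2.4 removes patients from the study when treatment stops, so part of the 15% is not missing at all. The calculation includes no covariates, whereas the planned GEE includes GOLD group, which the eCRF derives from exacerbation history, mMRC and CAT and so carries some baseline CAT information. At the correlation that fits the protocol's SD of change, the bias is at most half a point. No hypothesis is tested. All of this stands and limits the size; none of it justifies a trigger set above the planned dropout.

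Three stronger readings are tempting.
- **That GEE needs completely random dropout.** It does not. Loss may depend on modelled covariates, and with two visits and an unstructured correlation, loss depending on baseline CAT ≥10 status does little harm (step 8).
- **That missing covariates will cost the primary model its precision.** The documents give no covariate missing rates and do not say that incomplete patients are deleted. Under independent gaps and deletion, the loss 1 − (1 − p)^k runs from 5.9% (1% on each of 6 covariates) to 40.1% (5% on each of 10), so the answer is set by the assumption. Smoking and comorbidities already carry Unknown or Not evaluated levels, and the eCRF flags missing entries. Only the need for a rule stands, most concretely for pack-years.
- **That the SAP plans no other missing-data analysis.** Section 11.3.1 is unreadable, and the bases of several result tables are blacked out. The point is confined to the stated trigger.

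**Conclusion.** The point holds in a limited form. The imputation rule cannot start at the dropout the protocol plans, and the GEE outcomes then lack the protection claimed for the MMRM on the same score. The MMRM outcomes are not put in doubt under missing at random.

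For CAT ≥10, if loss follows the continuous baseline CAT, the bias at 15% is about 0.3 to 0.5 percentage points at correlation 0.17 and about 0.8 to 1.5 at correlation 0.6, on a true change of about −5. That is below the sampling half-width of roughly 3 points, and smaller again once intercurrent events are taken out of the 15%. The direction depends on who is lost. These sizes rest on the assumed CAT means, SD, correlation and dropout slopes, and on a model without covariates. It is an inexpensive improvement worth making, not a threat to the primary result.

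**What to change.** - Delete the 25% trigger in SAP 5.1 and 10.2. Make the two sections agree on whether the rule applies to variables or outcomes, and on whether imputation is done or merely examined.
- At any level of missingness, multiply impute Month-3 CAT and EQ-5D levels that are missing for non-IE reasons, using baseline data already collected (CAT, EQ-5D-5L, mMRC, the GOLD inputs, comorbidities, site). Derive CAT ≥10 from the imputed score, run the GEE in each completed data set, and combine the results. Keep the worst-value rule for intercurrent events as it is.
- Report the available-case GEE as a check, with its missingness assumption stated.
- Keep patients with incomplete covariates in every model: retain Unknown or Not evaluated as a category, set pack-years to 0 for never smokers, and impute other missing baseline covariates.

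The cost is some programming and an imputation model that must be written down in advance. No new data are needed.
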